## LIST OF ABBREVIATIONS

Abbreviation or Specialized Term	Definition
ADA	Anti-Drug Antibody
AE	Adverse event
AESI	Adverse Event of Special Interest
ALT	Alanine Aminotransferase
ARID1A	AT-rich interactive domain-containing Protein 1A
AST	Aspartate Aminotransferase
АТМ	Ataxia Telangiectasia Mutated
ATR	Ataxia Telangiectasia and Rad3-Related Protein
BICR	Blinded Independent Central Review
BILI	Total Bilirubin
BMI	Body mass index
BOR	Best Objective Response
BRAF	B-Rapidly Accelerated Fibrosarcoma Gene
BSR	Baseline Scaled Ratio
CI	Confidence Interval
COVID-19	Coronavirus Disease 2019
CR	Complete Response
CRF	Case Report Form
CSP	Clinical Study Protocol
CSR	Clinical Study Report
CTCAE	Common Terminology Criteria for AEs
CV	Coefficient of Variation
DCO	Data Cut-Off
DCR	Disease Control Rate
DoR	Duration of Response
DRM	Data Review Meeting
ECG	Electrocardiogram
ECOG	Eastern Cooperative Oncology Group
CCI	CCI

GCP	Good Clinical Practice
gCV	Geometric Coefficient of Variance
Gmean	Geometric Mean
gSD	Geometric Standard Deviation
HR	Hazard Ratio
CCI	CCI
ΙΟ	Immune-Oncology
ICF	Informed Consent Form
IDMC	Independent Data Monitoring Committee
IL	Item Library
IP	Investigational Product
IPD	Important Protocol Deviation
KIT	Proto-oncogene c-KIT
LDH	Lactic Acid Dehydrogenase
LLOQ	Lower Limit of Quantification
LVEF	Left Ventricular Ejection Fraction
MedDRA	Medical Dictionary for Regulatory Activities
max	Maximum
min	Minimum
MMRM	Mixed Model for Repeated Measures
MSI	Activating Mutations and Microsatellite Instability
MUGA	Multigated Acquisition
NA	Not Applicable
NE	Not Evaluable
NF1	Neurofibromatosis type 1
NTL	Non-Target Lesion
NR	Not Reportable
NRAS	NRAS proto-oncogene, GTPase
NS	No Sample
OAE	Other significant adverse event
ORR	Objective Response Rate
OS	Overall Survival
PD	Progressive Disease
PD-(L)1	Programmed Cell Death 1 Ligand
PFS	Progression Free Survival
CCI	CCI

CCI	CCI
CCI	CCI
РК	Pharmacokinetics
PR	Partial Response
PRO	Patient Reported Outcome
CCI	CCI
РТ	Preferred Term
RDI	Relative Dose Intensity
SAE	Serious adverse event
SAP	Statistical Analysis Plan
SD	Stable Disease
SE	Standard Error
SMQ	Standardized MedDRA Queries
SOC	System Organ Class
Std Dev	Standard Deviation
TL	Target Lesion
TLF	Tables Listings Figures
TACE	Transarterial Chemoembolization
TARE	Transarterial Radioembolization
CCI	CCI
TEAE	Treatment Emergent Adverse Events
CCI	CCI
ТОС	Table of Contents
TTR	Time to Objective Response
ULN	Upper Limit of Normal

## **AMENDMENT HISTORY**

AstraZeneca 12-Mar-2024

CATEGORY Change refers to:	Date	Description of change	In line with CSP?	Rationale
N/A	Click or tap to enter a date.	Initial approved SAP	N/A	N/A
Typo and missing author signature	7/27/2022	Fixed typo in 4.2.8.2.2 and added missing author signature which was missing in ed 1.0	yes	See description.
Update to interim analyses details	6/16/2023	Section 3.3 updated to cover additional supportive analysis which will be included for the interim analyses	N/A	See description.
Biopsy sub-study analysis	11/15/2023	Details of the biopsy sub- study have been removed from this SAP	yes	The biopsy sub-study will be covered in a separate SAP
Layout	11/15/2023	SAP layout updated for consistency with AZ Late Oncology TA SAP	Yes	Updated as Study now covered by AZ Late Oncology team
Timing of Analyses	11/15/2023	Descriptions of triggers for analyses to be performed updated	Yes	To reflect what was required for each analysis
Visit window information	11/15/2023	Table outlining visit windows removed The rule for calculating visit windows updated where there is an even number of days between visits	Yes	Inconsistency withing the SAP
Analysis Set definitions	11/15/2023	Added definitions of analysis sets used for interim analyses and corrected definitions for others	Yes	To endure all analysis sets used for tables, listings and figures were clearly defined within SAP

Important Protocol Deviations	11/15/2023	Added categories presented under AZ standard IPD table shell	Yes	updated to show how individual IPDs could be mapped to standard table
Definition of Best Objective Response added	11/15/2023	Added section defining endpoint and analysis to be performed	Yes	This is needed for determining Objective Response Rate
Definition of Disease Control Rate endpoint added	11/15/2023	Added section defining endpoint and analysis to be performed	Yes	This was interim analysis endpoint defined in CSP but previously missing from SAP
Exposure	11/15/2023	Duration of exposure and total actual exposure calculations updated Summary of dose omissions removed	Yes	Updated to be consistent with approach used on other ceralasertib studies
<adverse -="" delete="" event=""> Missing date imputations</adverse>	11/15/2023	Imputation rules for missing dates updated for consistency with AZ Late Oncology TA SAP Imputation for missing end dates of ceralacertib added	Yes	Updated as Study now covered by AZ Late Oncology team
Analysis of biomarker endpoints	11/15/2023	Methods of summarising/reporting data updated	Yes	Updated following internal AZ discussion

4.3, 4.4.4, 4.4.1	03/12/2024	Removal of subgroup analyses for TL size, reduction of sensitivity analyses, making biomarker outputs optional, CCI from exploratory analysis, imputation for completely unknown death date, subgroup analyses reduced.	yes	Reduction of outputs
-------------------	------------	--	-----	----------------------

## 1 INTRODUCTION

The purpose of this document is to give details for the statistical analysis of the main study of D533AC00001 supporting the clinical study report (CSR). The reader is referred to the clinical study protocol (CSP) and the case report form (CRF) for details of study conduct and data collection. This statistical analysis plan (SAP) is based on Amendment 2 of the CSP dated 14 March 2022. In the event of future amendments to the protocol, this SAP may be modified to account for changes relevant to the statistical analysis.

A separate SAP will be created for the biopsy sub-study

## 2 CHANGES TO PROTOCOL PLANNED ANALYSES

Not applicable

## **3** DATA ANALYSIS CONSIDERATIONS

#### **3.1** Timing of Analyses

The details of the analyses planned during the conduct of this study are outlined below and summarised in the following table.

#### Table 1: Summary of planned analyses

Analysis	Trigger	Scope
Interim Analysis	Once subjects are treated in the main study and have approximately weeks of follow-up	Safety data, efficacy data excluding overall survival (OS), Study Conduct until DCO
Interim Analysis	Once subjects are treated in the main study and have approximately weeks of follow-up	Safety data, efficacy data excluding OS, Study Conduct until DCO
Primary Analysis	Once all randomised subjects have had a minimum of months of follow-up after start of study intervention or discontinued from study, whichever occurs first.	All available data

Analysis	Trigger	Scope
	May be postponed to ensure a minimum of months median duration of follow-up.	
Repeated Primary Analysis	It is anticipated at least approximately ••• % of all randomised subjects will have progressed or died at the time of the primary analysis. However, if this is not the case, a later analysis for Progression Free Survival (PFS) may be conducted once approximately ••• % of all randomised subjects have progressed or died.	Optional Analysis
Analysis	Once approximately % of all randomised subjects have died or years from when the last subject starts treatment, whichever is earliest.	All available data

DCO: Data cut-off

Details of the interim analyses are given in Section 5.

The primary analysis of the ORR is conducted once all randomised subjects have had a minimum of months of follow-up after start of study treatment or have discontinued from the study, whichever occurs first. It is anticipated that the median duration of follow up for DoR is at least months at this point, however if not, then the primary analysis may be postponed to ensure a minimum of months median duration of follow up. At this primary analysis the CSR is written.

It is anticipated at least approximately 3% of all randomised subjects have progressed or died at the time of the primary analysis. However, if this is not the case, a later analysis for Progression Free Survival (PFS) may be conducted once approximately 3% of all randomised subjects have progressed or died. If later analyses are required an appendix to the SAP will be written.

A CCI analysis is conducted once approximately CO % of all randomised subjects have died, or years from when the last subject starts treatment, whichever is earliest. If the CCI analysis is performed Years from when the last subject starts treatment due to less deaths than assumed and CO % of PFS events have not been reached, then only the CCI analysis will be performed i.e. the primary analysis will not be repeated after the CCI analysis. The primary and CCI analyses may be combined if the required PFS and OS events are due to be reached at a similar time.

## **3.2** General Considerations

The below-mentioned general principles will be followed throughout the study:

- Summary tables are produced by treatment group. Total columns are produced for non-efficacy tables.
- Descriptive statistics will be used for all variables, as appropriate.
  - Continuous variables will be summarised by the number of observations, mean, standard deviation, median, upper, and lower quartiles where indicated, minimum and maximum. For log-transformed data (ie, pharmacokinetic [PK] concentration data) it is more appropriate to present geometric mean, coefficient of variation (CV), median, minimum, and maximum.
  - If data are available for less than 3 subjects, no summary statistics other than minimum, maximum and number of observations are presented.
  - Categorical variables will be summarised by frequency counts and percentages for each category. Unless otherwise stated, percentages will be calculated based on the analysis set population total, by treatment group and by timepoint as appropriate.
- For continuous data, the mean, standard deviation and median are rounded to one additional decimal place compared to the original data. Minimum and maximum are displayed with the same accuracy as the original data.
- Time-to-event variables will be presented using the Kaplan-Meier (KM) methodology, including median time calculated from the KM curves.
- For categorical data, percentages are rounded to one decimal place with the exception of 100% which is presented as a whole number.
- SAS® version 9.4 (or higher) and/or other validated software (as appropriate) will be used for the analyses. In case R is used, the R build version and the version of each used R package will be documented.

#### **3.2.1** Sample Size Determination

Confirmed objective response rate is the primary endpoint in this study. The primary analysis will be conducted once all randomized patients have had a minimum of months of follow-up after start of study treatment or have discontinued from the study, whichever occurs first. It is anticipated that the median duration of follow up will be at least months at this point, however if not, then the primary analysis may be postponed to ensure a minimum of months median duration of follow up. At this primary analysis the CSR will be written.

Each treatment arm is experimental and thus will be analyzed separately for ORR. The study will recruit approximately 100 patients in the ceralasertib and durvalumab combination therapy arm. With 100 patients the expected  $\bigcirc$  width of the  $\bigcirc$  % CI for ORR will be up to approximately  $\bigcirc$  % when the proportion of patients with an objective response is in the range  $\bigcirc$  % to  $\bigcirc$  %. For example, ORR  $\bigcirc$  % CI  $\bigcirc$  %,  $\bigcirc$  % CI  $\bigcirc$  %. The study will recruit approximately 50 patients in the ceralasertib monotherapy arm. With 50 patients, the expected  $\bigcirc$  width of the  $\bigcirc$  % CI for ORR will be up to approximately  $\bigcirc$  % or % CI for ORR will be up to approximately  $\bigcirc$  %. For example, ORR  $\bigcirc$  % to  $\bigcirc$  %. For example, or % with an objective response is in the range  $\bigcirc$  % to  $\bigcirc$  %. For example, ORR  $\bigcirc$  % to  $\bigcirc$  %. For example, or % with an objective response is in the range  $\bigcirc$  % to  $\bigcirc$  %. For example, ORR  $\bigcirc$  % to  $\bigcirc$  %. For example, or % when the proportion of patients with an objective response is in the range  $\bigcirc$  % to  $\bigcirc$  %. For example, ORR  $\bigcirc$  % to  $\bigcirc$  %. For example, or %,  $\bigcirc$  % CI  $\bigcirc$  %. The sample size of the ceralasertib monotherapy arm may be expanded up to a total of approximately 100 patients. This would occur in the event an efficacy signal is observed, and subject to a protocol amendment.

There is no standard of care after anti-PD-(L)1 immunotherapy for the intended patientpopulation. Objective response rate for chemotherapy treatment options for patient second line and beyond, post-ipilimumab, are previously reported to be 4% (95% CI 2%, 9%) and 10% (95% CI 5%, 16%). There is no prospective clinical trial data on response rates forchemotherapy specifically in the post CPI-resistant setting. An ORR of % is considered an upper limit of expected response rate for alternative available treatment options for theintended patient population in this study. Per the proposed Phase 2 study design, with100 evaluable patients in the ceralasertib and durvalumab combination therapy arm, successwill be achieved if a minimum ORR of % is observed, for which the %% exact CI wouldbe (CCI %, CCI %).

A secondary objective is to compare the ORR between the two treatment arms. With150 patients (100 patients randomized to ceralasertib and durvalumab combination therapyarm and 50 patients randomized to ceralasertib monotherapy), there will be at least % power at a % of % to detect a difference in ORR, assuming an ORR for ceralasertib plus durvalumab of % and an ORR for ceralasertib monotherapy of %.

It is anticipated at least approximately % of all randomized patients will have progressed or died at the time of the primary analysis. However, if this is not the case, a later analysis for PFS may be conducted once approximately % of all randomized patients have progressed or died.

analysis will be conducted once approximately % of all randomized patients have

died, or years from when the last patient starts treatment, whichever is earliest.

#### **3.2.2** Study Treatment

The main study is a Phase 2, randomised, open-label, multicentre, international study assessing the efficacy and safety of ceralasertib and ceralasertib plus durvalumab in subjects with unresectable or advanced melanoma and primary or secondary resistance to programmed death-ligand 1 [PD-(L)1] inhibition. Approximately 150 subjects are randomised, at a 2:1 randomisation ratio (approximately 100 subjects in Arm 1 and approximately 50 subjects in Arm 2) to the following intervention groups:

- Arm 1: Ceralasertib 240 mg BD oral tablets, from Days 1 to 7 plus durvalumab 1500 mg Day 8, IV infusion, Q28D, until progressive disease, (confirmed RECIST 1.1-defined radiological progression), unacceptable toxicity, withdrawal of consent, or if a study treatment discontinuation criteria is met.
- 2. Arm 2: Ceralasertib 240 mg BD oral tablets, from Days 1 to 7, Q28D, until progressive disease, (confirmed RECIST 1.1-defined radiological progression), unacceptable toxicity, withdrawal of consent, or if a study treatment discontinuation criterion is met.

Crossover within the study is not be permitted. There is no defined maximum treatment duration for the treatment arms as the subjects receive study treatment until progressive disease (RECIST 1.1-defined radiological progression), unacceptable toxicity, withdrawal of consent, or if a study treatment discontinuation criterion is met.

Randomisation into the treatment arms is stratified by:

• Resistance to prior immune-oncology treatment (primary/early relapse in adjuvant setting vs secondary resistance).

• Baseline lactate dehydrogenase (LDH) expression (below and equal to the upper limit of normal vs above upper limit of normal).

#### 3.2.3 Baseline

In general, the last observed measurement prior to first dose of study intervention will be considered the baseline measurement. For efficacy variables, baseline is defined as the last observed measurement prior to randomisation

For assessments on the day of first dose where time is not captured, a nominal pre-dose indicator, if available, serves as sufficient evidence that the assessment occurred prior to first dose. Assessments on the day of the first dose where neither time nor a nominal predose indicator are captured is considered prior to the first dose if such procedures are

required by the protocol to be conducted before the first dose. If no value exists before the first dose/administration, then the baseline value is treated as missing..

If two measurements are equally eligible to assess patient status at baseline (eg, two assessments both on the same date with no time recorded), the average is used as the baseline value. For non-numeric laboratory tests (ie, some of the urinalysis parameters)where taking the average is not possible, the best value (value closest to none/normal/negative) is used as baseline as this is most conservative. In the scenario where there are two eligible baseline assessments recorded on the same day, one with time recorded and the other without time recorded, the one with the time recorded is selected as baseline. Where safety data will be summarised over time, time on study is calculated in relation to date of first treatment.

In all summaries change from baseline variables are calculated as the post-treatment value minus the value at baseline. The percentage change from baseline is calculated as (post-baseline value - baseline value)/(baseline value) x 100. For any endpoint subjected to log transformation, the change from baseline calculated and summarised on the log scale are back-transformed and presented as a 'baseline scaled ratio' (BSR). Percentage change is then calculated as (BSR - 1)  $\times$  100.

## 3.2.4 On-treatment

For the purposes of summarizing safety data assessed at visits, in addition to baseline data, only on-treatment data are included in the summary tables. On-treatment data is defined as data on/after the first dose of study treatment and with assessment date up to and including the date of last study treatment + 30 days (safety follow-up) for ceralasertib monotherapy or the date of last study treatment + 90 days (safety follow-up) for ceralasertib and durvalumab combination, and prior to the start of any subsequent anti-cancer therapy.

The on-treatment period therefore comprises of the treatment period (first administration of any study treatment to and including last day of administration of any study treatment) and the safety follow-up period (30 days after last administration for ceralasertib monotherapy or 90 days after last administration for ceralasertib and durvalumab combination), and prior to the start of any subsequent anti-cancer therapy.

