#### Irradiated lesions/lesion intervention

Previously irradiated lesions (i.e. lesion irradiated prior to entry into the study) are recorded as NTLs and should not form part of the TL assessment.

Any TL (including lymph nodes), which has had intervention during the study (for example, irradiation / palliative surgery / embolization but note this does not include protocol specified biopsies), are handled in the following way. Once a lesion has had intervention then it is treated as having intervention for the remainder of the study noting that an intervention most likely shrinks the size of tumours:

- Step 1: the diameters of the TLs (including the lesions that have had intervention) are summed and the calculation is performed in the usual manner. If the visit response is PD, this remains as a valid response category.
- Step 2: If there is no evidence of progression after step 1, the lesion diameter (for those lesions with intervention) will be treated as missing and if ≤1/3 of the TLs have missing measurements then scale up as described in the 'Scaling' section below. If the scaling results in a visit response of PD then the patients will be assigned a TL response of PD.
- Step 3: If, after both steps, PD has not been assigned, then, if appropriate (i.e. if ≤1/3 of the TLs have missing measurements), the scaled sum of diameters calculated in step 2 will be used, and PR or SD will be assigned as the visit response. Patients with intervention will be evaluable for CR as long as all non-intervened lesions are 0 (or <10mm for lymph nodes) and the lesions that have been subject to intervention have a value of 0 (or <10mm for lymph nodes) recorded. If scaling up is not appropriate due to too few non-missing measurements, then the visit response will be set as NE.

At subsequent visits, the above steps are repeated to determine the TL and overall visit response When calculating the previous minimum, lesions with intervention will be treated as missing and scaled up (as per step 2 above).

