#### 4.3.1.2 Derivations

A confirmed response of CR/PR means that a response of CR/PR is recorded at 1 visit and confirmed by repeat imaging not less than 4 weeks after the visit when the response was first observed with no evidence of progression between the initial and CR/PR confirmation visit. Data obtained up until progression, or last evaluable assessment in the absence of progression, are included in the assessment of ORR. Also only data obtained before the start of subsequent anticancer treatment (excluding radiotherapy) are included. Therefore both visits contributing to a confirmed response must be prior to progression and prior to subsequent anticancer treatment.

In the case where a subject has two non-consecutive visit responses of PR, then, as long as the time between the 2 visits of PR is greater than 4 weeks and there is no PD between the PR visits, the subject is defined as a responder. Similarly, if a subject has visit responses of CR, NE, CR, then, as long as the time between the 2 visits of CR is greater than 4 weeks, then a best response of CR is assigned.

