# 4.3.2 Best Objective Response

#### 4.3.2.1 Definition

Best objective response (BoR) will be calculated based on the overall visit responses from each RECIST assessment, described in section 3.2.10. It is the best response a patient has had following randomisation, but prior to starting any subsequent cancer therapy and up to and including RECIST progression or the last evaluable assessment in the absence of RECIST progression.

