#### 4.3.8.1 Definition

The TL tumour size and percentage change from baseline in the sum of TL tumour size at each assessment are calculated. The best absolute change in TL tumour size from baseline (i.e. depth of response) is the largest decrease from baseline or the smallest increase from baseline in the absence of reduction and includes all assessments:

- up to and including the first visit at which the overall visit response is PD,
- prior to death in the absence of progression,
- prior to the start of subsequent anti-cancer therapy (excluding radiotherapy);
- or up to and including the last evaluable RECIST assessment if the subject has not died, progressed or started subsequent anti-cancer therapy.

Each post-baseline disease assessment for a subject that meets the following conditions are included: all target lesions identified at baseline have measurements recorded at the current visit (i.e. they cannot be not done or not evaluable). If a lesion is recorded as  $\leq 5$  mm then this will be used in the calculations.

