#### 4.3.12.2 Adverse Events

# 4.3.12.2.1 Definitions and Derivations

The Medical Dictionary for Regulatory Activities (MedDRA) (version 25 or higher) is used to code the AEs. AEs are graded according to the National Cancer Institute Common Terminology Criteria for AEs (CTCAE) (version 5.0).

Treatment emergent adverse events (TEAEs) are all AEs which onset or worsen in severity following the first administration of IP within the duration of the treatment period, up to

and including 30 days after the last dose of study treatment for ceralasertib monotherapy or 90 days after last dose of study treatment for ceralasertib and durvalumab combination, and prior to the start of any subsequent anti-cancer therapy,. Worsening in severity is determined by comparison with the pre-treatment CTCAE grade of the AE recorded closest to the start of dosing.

AEs with a missing start time or where time is not collected, which occur on the same day as first IP administration, are reported as treatment emergent.

For rules on missing or partial dates, see Section 3.4.6.

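### The safety windows close at any subsequent anti-cancer therapy without the radiotherapy exception that ORR and best percentage change carry, so radiotherapy can cut post-dose TEAE capture

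*SAP*

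**What the plan says.** Section 3.2.4 of the main-study SAP keeps visit-based safety data up to "the date of last study treatment + 30 days (safety follow-up) for ceralasertib monotherapy". In the combination arm the corresponding limit is 90 days. In both arms the data must also fall before later therapy: "and prior to the start of any subsequent anti-cancer therapy". Section 4.3.12.2.1 applies the same limit to TEAEs: "combination, and prior to the start of any subsequent anti-cancer therapy".

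Two efficacy sections use the same class of therapy and take radiotherapy out of it. For ORR, section 4.3.1.2 says "Also only data obtained before the start of subsequent anticancer treatment (excluding radiotherapy) are included". For best percentage change, section 4.3.8.1 includes assessments "prior to the start of subsequent anti-cancer therapy (excluding radiotherapy").

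Best objective response does not follow ORR. Section 4.3.2.1 counts responses after randomisation "but prior to starting any subsequent cancer therapy", with no exception for radiotherapy, and 4.3.2.2 repeats that cut-off.

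The SAP foresees irradiation on study. The lesion-intervention rules in 3.2.10 cover any target lesion "which has had intervention during the study (for example, irradiation / palliative surgery / embolization"), with later visits still assessed.

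**The concern.** An exception for radiotherapy is needed in 4.3.1.2 and 4.3.8.1 only if radiotherapy would otherwise belong to subsequent anti-cancer therapy. The safety definitions use that class, strengthened by *any*, without the exception. A programmer who follows the text will therefore close the safety windows at radiotherapy and keep the ORR and best-change windows open. No reason for the difference is given.

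At stake is where an event appears. Under 4.3.12.2.2, TEAEs are summarised and other AEs are only listed, and SAEs are summarised in the same way as TEAEs. An AE or SAE that starts after radiotherapy but within 30 or 90 days of the last dose would move from the incidence tables to a listing. The combination arm has the longer follow-up, and so more to lose.

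**Working it through.** The SAP states no figure to reproduce. The check compares the rules and applies simple date arithmetic.

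**Which windows close at radiotherapy, read literally**

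| Output | Section | Closed by radiotherapy? |
|---|---|---|
| Visit-based safety data | 3.2.4 | Yes |
| TEAEs, and SAEs summarised like them | 4.3.12.2.1, 4.3.12.2.2 | Yes |
| Laboratory abnormalities | 4.3.12.3.2 | No; runs to the last on-study assessment |
| Deaths | 4.3.12.2.2 | No; summarised for all subjects |
| AEs that are not treatment emergent | 4.3.12.2.2 | Listed only |
| ORR | 4.3.1.2 | No; exempted by name |
| Best percentage change | 4.3.8.1 | No; exempted by name |
| Best objective response | 4.3.2.1, 4.3.2.2 | Yes |

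**Follow-up lost when radiotherapy starts after the last dose**

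Let radiotherapy start *k* days after the last dose. Only days before that start count, so *k* − 1 post-dose days are kept.

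- Monotherapy: days lost = 30 − (*k* − 1) = 31 − *k*, for *k* from 1 to 30.
- Combination: days lost = 90 − (*k* − 1) = 91 − *k*, for *k* from 1 to 90.
- Illustration, *k* = 15: 16 of 30 days lost (monotherapy), 76 of 90 lost (combination).

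**Effect of a partial date**

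Section 3.2.8 imputes a subsequent-therapy start with a missing day to the day after treatment when the month matches the treatment-end month. It does the same for a missing day and month when the year matches. Then *k* = 1, and the loss is 30 of 30 or 90 of 90 days. If the start day itself were counted, one day would remain. This happens however late in that month or year the radiotherapy was actually given.

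**Radiotherapy during dosing**

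The wording does not settle this. Three places point to *subsequent* meaning after study treatment:

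- The second paragraph of 3.2.4 builds the period from the whole of treatment plus follow-up.
- The imputation in 3.2.8 presumes a start after treatment ends.
- Section 4.2.7.1 handles radiotherapy dates alongside prior and concomitant therapy, where concomitant means sharing at least one day with study treatment.

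If on-dosing radiotherapy were nevertheless counted, events later in the treatment period would be lost as well.

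**ORR against best objective response**

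Take a subject with a PR at week 8, radiotherapy before week 16, and a PR at week 16. Under 4.3.1.2 both scans count, they are more than 4 weeks apart, and the subject is a responder. Under 4.3.2.1 and 4.3.2.2 the week 16 scan falls after the cut-off, so the PR is unconfirmed and is classed under SD. The two tables can then give different numbers of confirmed responders.

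**The case against.** The strongest objection is that safety and efficacy windows may properly differ. A safety cut-off protects attribution of events to study drug. A response cut-off protects attribution of tumour shrinkage. PFS (4.3.9.1) and OS (4.3.10.1) deliberately run through later therapy. This stands: a difference is not an error in itself. It does not explain why the same undefined class has radiotherapy removed in some sections and not in others.

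A reader might infer that benefit after irradiation is counted while harm is not. The SAP does not support that as a general pattern. Deaths, listed AEs and the laboratory-abnormality presentation continue past the cut, and 3.2.6 uses all post-baseline values for subject-level extremes. On the benefit side, best objective response stops at any later therapy. In the investigator derivation, 3.2.10 sets an irradiated target lesion to missing and scales the sum, or makes the visit NE, unless PD is met; CR still requires that lesion to be recorded as 0, or below 10 mm for a node. That restriction is written for investigator data. Section 4.3 says BICR visit responses need no programmatic derivation, so for the primary endpoint the SAP itself states no equivalent rule.

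A reader might also infer that one palliative fraction in mid-treatment wipes out most of a subject's safety record. That requires concomitant radiotherapy to count as subsequent therapy, which 3.2.8 and 4.2.7.1 argue against. A loss of that size is not established.

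**Conclusion.** The point holds as an undefined term applied inconsistently, with a specific consequence for safety tabulation. Per subject, radiotherapy after the last dose can remove up to 30 days (monotherapy) or 90 days (combination) of post-dose TEAE and visit-based capture, and partial-date imputation can produce that maximum. More would be lost only if radiotherapy during dosing is also caught, which the SAP leaves open and on balance points against.

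This rests on radiotherapy belonging to subsequent anti-cancer therapy. The exceptions in 4.3.1.2 and 4.3.8.1 imply it, but no definition states it. No population-level loss can be given, because the SAP contains neither a rate nor a timing of radiotherapy. The correction is a cheap improvement to the TEAE, SAE and visit-based tables; it does not touch the ORR rule itself.

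**What to change.** - In 3.2.4 (both paragraphs) and 4.3.12.2.1, add *excluding radiotherapy* to the cut-off, so that radiotherapy during or after dosing ends neither the on-treatment period nor the TEAE period.
- Use the same definition in 4.3.2.1 and 4.3.2.2, so that best objective response agrees with ORR in 4.3.1.2.

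The cost is a wording change and the matching programming. The downside is that some radiotherapy-related toxicity will enter the all-cause TEAE tables; it stays separable through the IP-related tables planned in 4.3.12.2.2.
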